## **Specific Aims and Hypotheses**

#### Specific Aims and Hypotheses

#### Primary Outcome Measure:

(1) Cannabis withdrawal (mood, sleep quality and duration, food intake)

(2) Cannabis relapse defined as (1) time to any MJ use as recorded by the timeline follow back method and

confirmed by urine metabolite levels, or (2) time to dropout, whichever comes first, and (3) medication compliance (% of pills taken) or time to discontinuation. Participants who relapse will continue in the trial to obtain secondary outcome measures.

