## Table 3: Outpatient Study Assessments

	X once weekly; XX twice weekly	Screening	Baseline	Week 1	Week 2	Week 3	Week 4	Week 5	Week 6	Week 7	Week 8	Week 9	Week 10	Week 11	Week 12
	Medical History and Physical Examination	x													
	Pregnancy, serum	x													
	Pregnancy, urine		x				х				х				х
	Psychiatric Evaluation	x													
5	Serum Laboratory Examination	x					х				х				х
latic	Urinalysis	x					х				х				х
Medical Evaluation	Urine Toxicology	x	x	х	X X	x x	x x								
dical	Urine Fluorometry (quantitative riboflavin)			x	X X	X X	x x								
Med	Vital signs (weight, pulse, blood pressure, and temperature)		x	x	X X	x x	x x								
	CIWA-BZD									Х	Х	Х	Х		
	Clinical Global Improvement Scale (CGI)- Observer		x	х	x	x	х	х	x	x	х	x	х	x	x
	C-SSRS	x	x		x		х		х		х		х		х
	Hamilton Anxiety Scale (HAM-A)		x		x		х		х		х		х		х
Interview	MINI International Neuropsychiatric Interview	x													
ter	Structure Pill Count Interview			х	x	x	х	х	х	x	х	х	х	х	х
_	Systematic Assessment for Treatment and Emergent Events (SAFTEE)		x	x	x	x	x	x	x	x	x	x	х	x	x
	Timeline Follow-Back (TLFB)	x	x	х	x	x	х	х	х	x	х	х	х	х	х
	Treatment Services Review (TSR)		х	х	x	x	х	х	х	x	х	х	х	х	х
	Clinical Global Impression (CGI)-Self		x	х	x	x	х	х	x	х	х	х	х	х	х
Self- Report	Marijuana Craving Questionnaire (MCQ)		х	х	x	x	х	х	х	x	х	х	х	х	х
Se Rep	Marijuana Withdrawal Checklist (MWC)		x	х	x	x	х	х	x	x	х	х	х	х	х
	Pittsburgh Sleep Quality Index (PSQI)		х	х	х	х	х	х	х	х	х	х	х	х	х

Tabl	e 1: Inpatient F					
Day	1	2	3	4	5	6
Study Groups	Move-in	Witha	Irawal, cognition	, abuse liability		Move-out
Clonazepam (mg/day)	1.0	2.0	2.0	2.0	2.0	2.0
Placebo (mg/day)	0.0	0.0	0.0	0.0	0.0	0.0

Study Groups	Week 1 Days 6-7 (outpatient)	Weeks 2-7 Days 8-49 (outpatient)	Week 8 Days 50-51 (outpatient taper)	Week 8 Days 52-54 (outpatient taper)	Week 8 Days 55-56 (outpatient taper)	Week 9-12 Days 57-84 (outpatient obervations)
Experimental Group	clonazepam capsules 1 mg twice daily	Clonazeapam capsules 1 mg twice daily	Clonazepam capsules 0.5 mg QAM and 1 mg QHS	Clonazepam capsules 0.5 mg QAM and 0.5 mg QHS	Clonazepam capsules 0.5 mg QHS	No study medication
Placebo Group	Placebo capsules Twice daily	Placebo capsules twice daily	Placebo capsules twice daily	Placebo capsules twice daily	Placebo capsule QHS	No study medication

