Study: # 7343 entitled EFFECT OF CLONAZEPAM ON CANNABIS WITHDRAWAL AND RELAPSE IN TREATMENT-SEEKING PATIENTS: COMBINED INPATIENT/OUTPATIENT STUDY

PI: [name].

NCT# NCT02913924

Statistical Analysis Plan (Grant): 9/19/2013

Amended 4/15/2016 (DSMP)

Grant Submission U54 DA037842: 9/19/2013

3. Data Analysis a. Outcome Measures and Covariates

i. Primary outcome measures: 1) Cannabis use: The time to sustained relapse defined as 5 days of cannabis use over a 7 day period as recorded by the Timeline Followback method and confirmed by creatinine-normalized quantitative urine THC levels, or time to dropout of study, whichever comes first (survival outcome).

ii. Secondary outcome measures: These measures are designed to capture changes in cannabis consumption patterns and other symptoms not measured by the primary outcome measures.

1) Abstinence during the final two weeks (study weeks 11 and 12) of the study (dichotomous)

2) Retention in treatment (survival outcome)

3) Days per week of cannabis use (continuous longitudinal)

4) Cannabis withdrawal: measured by weekly Marijuana Withdrawal Checklist (continuous longitudinal)5) Cannabis craving: measured by weekly Marijuana Craving Questionnaire (continuous longitudinal)

6) Sleep disturbance: measured by the Medical Outcomes Study—Sleep Scale (continuous longitudinal)

iii. Covariates: 1) Demographic characteristics (e.g., gender, age) 2) Baseline severity of cannabis use (measured by the quantity of cannabis per using day at baseline)

iv. Other measures: Adverse effects, as measured by the Systematic Assessment for Treatment and Emergent Events (SAFTEE), will be assessed, including potential effects on compliance and outcome.

b. Sample Size and Randomization: The Research Core will supervise randomization procedures. A total of 72 patients will be recruited over a 2.5-year period and randomized to the double-blind treatment trial, with 36 patients randomized to each of the two treatment groups, nabilone/XR-NTX arm and placebo arm. The randomization sequence will be balanced in blocks of random size (2, 4, 6) to prevent clinicians from guessing what the next patient's treatment might be.

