d. Significance Testing and Preliminary Analyses: All tests for main effects will be performed at twotailed significance α =5%. Before performing specific analyses (described below), we will examine all variables for outliers. The distributions of all continuous variables will be checked for normality, and transformations will be employed, if necessary, before applying specific parametric techniques. The distribution of demographic variables (ethnicity, gender, age) and other covariate measures of at baseline in the treatment arms will be examined and described in terms of means, standard deviations, proportions and 95% confidence intervals. The covariates (specified in Section 3.a.iii) may be associated with treatment outcome. For this reason, we will adjust for these covariates in all models used to test the study hypotheses. These covariates will be included in all models as main effects regardless of their statistical significance or whether they differ between treatment groups. In the secondary analyses, we will adjust also for baseline value of the outcome variable where appropriate. This adjustment will be based on the inclusion of main effects for the baseline.

e. Hypotheses Testing i. Primary hypotheses:

Hypothesis 1: Nabilone and XR-NTX will significantly increase time to relapse as compared to placebo. The following Cox Proportional Hazards model will be used: (1) $\log{hi(t)} = \log{h0(t)} + \beta 1 I J + \beta 2 U J J$ where hij(t) is the hazard for individual i in the treatment group j at time t; h0(t) is the baseline hazard function; Uj is the vector of covariates; and I J is the indicator variable for treatment with nabilone and XR-NTX. Significant I J indicates that the hazard rate of each treatment group is different. ii. Secondary hypotheses:

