C. DATA MANAGEMENT AND ANALYSIS C1. Data Acquisition and Transmission Research assistants trained in behavioral observation techniques will assist in data collection during laboratory sessions. Subjective responses, performance effects, food intake and sleep will be obtained electronically using our custom-designed software programs. Some data (e.g., sleep questionnaires) will be recorded manually, and then entered into an Excel spreadsheet. C2. Data Entry Methods As noted above, a portion of the data is automated and a portion is recorded on data sheets, and transferred manually to an Excel spreadsheet. C3. Data Analysis Plan Subjective effects, food intake, sleep, and task performance will be analyzed using repeated measures analysis of variance (ANOVA) models with planned comparisons calculated with SUPERANOVA, SPSS or SYSTAT packages. We will use a cluster analysis of peak subjective effects ratings to reduce the overall number of comparisons (Haney et al., 2013a,b). Tests of differences will be based on F-statistics with degrees of freedom corrected, depending on the observed within-subject correlation of the measures, using the method of Huynh and Feldt. Planned contrasts will be single degree of freedom comparisons using the appropriate interaction error term. Results will be considered statistically significant at p < 0.05, using 2- tailed tests. The primary analyses in this study will be on the intent-to-treat (ITT) sample, i.e. on all randomized patients. Cannabis consumption and cannabis abstinence, are assessed repeatedly over time and we will try to collect them at all study assessment points. We will account for unobserved data by examining the primary outcome variables using longitudinal mixed effects models (MEM) (Brown & Prescott, 1999; Diggle, et al., 2002) using PROC GLIMMIX in SAS[®]. MEMs do not require complete measurements data to estimate the outcome variable. The inferences from analyses with missing data are valid provided that they are "missing at random" (Little & Rubin, 2002). 'Missing at random' (i.e the missing mechanism does not depend on the value of the unobserved outcome) is untestable in most medical research and in our study as well. One can assume either parametric or semiparametric models for the missingness that does depend on the unobserved outcome value and do the analysis (Diggle & Kenward, 1994; Kenward, 1998; Liu, et al., 1999; Rotnitzky, et al., 1998; Scharfstein, et al., 1999). Comparison of the inferences from assuming various models for the missingness provides a measure of the validity of the efficacy estimate from the model that assumes missing 'at random'. One can also compute a local sensitivity index which measures the change in the estimated treatment effect in a neighborhood of the 'missing at random' model for missingness (Rotnitzky, et al., 2001). We plan to perform a sensitivity analysis based on these two approaches to assess the effect of the assumption of missing 'at random' on the inference.

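### SAP C3 specifies no baseline-score adjustment for the primary inpatient withdrawal analysis, although usable scores are scheduled at Baseline: a possible loss of precision, of unknown size

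*SAP*

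**What the plan says.** The Protocol (Specific Aims and Hypotheses) lists as a primary outcome "1) Cannabis withdrawal (mood, sleep quality and duration, food intake"), and SAP A2 repeats it. Inpatient effects are measured on days 2 to 5, after a first capsule on the evening of day 1 (Protocol, Study Procedures).

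Two statements in SAP C3 bear on the model:

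- "Subjective effects, food intake, sleep, and task performance will be analyzed using repeated measures analysis of variance (ANOVA) models with planned comparisons", with Huynh-Feldt correction and single-degree-of-freedom contrasts.
- "We will account for unobserved data by examining the primary outcome variables using longitudinal mixed effects models (MEM").

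Neither statement names a covariate or a baseline score.

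Covariate rules appear only in SAP Section 3. Section 3.d says "we will adjust for these covariates in all models used to test the study hypotheses". The list in 3.a.iii is demographics plus "Baseline severity of cannabis use (measured by the quantity of cannabis per using day at baseline"). Section 3.d then adds: "In the secondary analyses, we will adjust also for baseline value of the outcome variable where appropriate". Section 3 is written for a different treatment and sample size, "with 36 patients randomized to each of the two treatment groups, nabilone/XR-NTX arm and placebo arm", and nothing carries its rules over to C3.

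Protocol Table 3, the outpatient schedule, marks the Marijuana Withdrawal Checklist (MWC), Marijuana Craving Questionnaire (MCQ), Pittsburgh Sleep Quality Index (PSQI) and Hamilton Anxiety Scale (HAM-A) in a Baseline column before Week 1.

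**The concern.** The comparison that SAP A4 powers for withdrawal is clonazepam against placebo in different patients, 40 per arm. In such a comparison, stable differences between patients add to the error of the treatment contrast, and chance imbalance at entry moves the estimate. A score taken before dosing can remove part of both. The plan schedules such scores but does not say that they enter the model for a primary outcome.

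At stake is power for that outcome. The stated power of over 90% rests on an SD and a correlation from earlier studies that are not reported, so a reader cannot tell whether there is precision to spare. Leaving covariates open also allows them to be chosen after the data are seen.

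**Working it through.** **Inputs from the documents.** N = 80, a single contrast at 0.05, a 25% decrease and power above 90% (SAP A4); 40 per arm (SAP A4, relapse calculation); two-tailed tests (SAP C3); 60 completers (Protocol, Description of Subject Population). **Assumed, because not given:** the SD, and the correlation r between the baseline score and the analysed contrast.

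**1. The plan's own figure.** Power above 90% cannot be reproduced without the SD, so it is solved backwards with the two-sample normal approximation. The standardised difference needed is d = (1.960 + 1.282) × √(2/40) = 0.725. The SD of the contrast must therefore be at most 0.25/0.725 = 34.5% of the placebo mean (29.9% with 30 completers per arm). With SD at 30, 40, 50 or 60% of the placebo mean, power is 96.1, 79.8, 60.9 or 46.2%. The claim can be neither confirmed nor refuted.

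**2. Effect of a baseline covariate.** Residual variance is multiplied by 1 − r². The effective d becomes d/√(1 − r²), and 80 adjusted patients carry the information of 80/(1 − r²) unadjusted ones.

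| r | 1 − r² | Equivalent N | Power if 90% unadjusted (normal) | Power if SD is 50% of placebo mean (noncentral t) |
|---|---|---|---|---|
| none | 1.00 | 80 | 90.0% | 59.8% |
| 0.2 | 0.96 | 83 | 91.1% | 61.6% |
| 0.3 | 0.91 | 88 | 92.5% | 63.9% |
| 0.5 | 0.75 | 107 | 96.3% | 72.2% |
| 0.7 | 0.51 | 157 | 99.5% | 87.1% |

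For the last column the normal approximation gives 60.9% unadjusted, then 62.6, 65.0, 73.3 and 87.9%. The choice of method moves the figures by about one point.

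**3. Repeated days.** If the contrast is the mean of four inpatient days, with the same correlation ρ between all occasions including baseline, the unadjusted variance is (1 + 3ρ)/4 and the adjusted variance is (1 + 3ρ)/4 − ρ². The ratio is 0.90, 0.81, 0.60 or 0.37 at ρ = 0.2, 0.3, 0.5 or 0.7. Averaging over days therefore does not remove the gain.

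**4. Cost of the covariate.** One covariate takes one degree of freedom (77 instead of 78), which changes power by about 0.02 percentage points.

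**5. Timing of Baseline.** The dosing schedule (Protocol Table 2) counts days 6-7 as Week 1 and days 8-49 as Weeks 2-7, so Week 1 starts on day 1. A Baseline column before Week 1 then implies a score taken before dosing. No date or day is stated.

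**The case against.** The strongest reply is that C3 is silent on covariates and never calls its analysis unadjusted. Read literally, 3.d already places demographics and baseline cannabis quantity in every hypothesis-testing model. C3 also names mixed models, so the choice of model is itself open. All of this stands. A reader might infer that the plan commits to an unadjusted ANOVA, and the documents do not support that. They do leave the gap: on no reading does a baseline withdrawal or sleep score enter a primary analysis.

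Second, the gain may be small. Participants are near-daily users at entry, while the outcome is withdrawal during inpatient abstinence, so r may be low. At r of 0.2 to 0.3 the variance falls by only 4 to 9%. This stands and is why the low end is shown.

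Third, C3 refers to an interaction error term. In a group-by-day contrast, stable patient differences already cancel, and a baseline main effect would add little. This limits the gain to contrasts between arms, at a given day or averaged over days. SAP A4 describes its power as medication against placebo, which is such a contrast.

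Fourth, the Table 3 scales belong to the outpatient schedule. No baseline is listed for food intake or objective sleep, and Baseline is not expressly dated before the first capsule. These points narrow the fix but do not remove it.

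**Conclusion.** The point holds as a gap in specification with a possible cost in precision. Randomisation keeps a comparison without baseline adjustment valid, so a reader who infers bias or a wrong published figure goes further than the documents allow. So does one who takes a large gain as established: the range runs from 4% less residual variance at r = 0.2 to 49% at r = 0.7, and neither r nor the SD is in the plan. The power gain is about 1 to 9.5 points if the stated 90% is just met, and about 2 to 27 points if the SD is 50% of the placebo mean. These figures assume 40 per arm, a contrast between arms and a score taken before dosing. The change is worth making because the outcome is primary and the cost is negligible even if r is low.

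**What to change.** In SAP C3:

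- Prespecify the Table 3 baseline score as a covariate in the between-group model: MWC for mood and withdrawal ratings, MCQ for craving, and PSQI for sleep ratings and, as the closest available measure, for objective sleep.
- Confirm that this baseline is taken before the first capsule on day 1.
- State that the 3.a.iii covariates required by 3.d also apply to C3. For food intake, which has no listed baseline, use these alone.
- State whether the repeated-measures ANOVA or the mixed model is the primary analysis of inpatient withdrawal, and report the SD and correlation behind the power statement in A4.

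This is a free improvement: a few sentences in the SAP and a check of the Baseline date, with no new patient, visit or instrument.

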f. Power Analysis: The sample size of 72 was chosen to ensure sufficient power (at least 80%) of a twosided test with level of significance α =0.05 for detecting difference between the two experimental treatments with respect to time to relapse, based on the Cox proportional hazards model. We expect that the nabilone and XR-NTX group will have greater time to relapse than the placebo group. The rate of retention for the placebo group at 12 weeks can be expected to be 15% based on our prior studies. With 36 per arm, we will be able to detect a difference in retention (without relapse) rates between placebo versus nabilone and XR-NTX of approximately 25% (i.e. 15% on placebo vs 39.6% on nabilone and XR-NTX). This corresponds to a hazard ratio of 0.49 (Machin et al. 1997). The proposed sample size will also enable us to estimate the retention rate of the treatment group with a 95% confidence interval, ±15%, in the worst case. The computation above was performed assuming that the covariates (i.e., baseline cannabis use and age) do not have a predictive power. The 25% rate difference is consistent with a medium to large sized effect, which is what we are seeking in this early Phase II trial. This represents an effect that would be clinically meaningful and likely to make a substantial impact on the success of XR-NTX treatment in clinical practice A2. Primary and Secondary Outcome Measures Primary Outcome Measure: (1) Cannabis withdrawal (mood, sleep quality and duration, food intake) (2) Cannabis relapse defined as (1) time to any MJ use as recorded by the timeline follow back method and confirmed by urine metabolite levels, or (2) time to dropout, whichever comes first, and (3) medication compliance (% of pills taken) or time to discontinuation. Participants who relapse will continue in the trial to obtain secondary outcome measures. Secondary Outcome Measures: (1) Abuse liability (medication liking, desire to take again) (2) Cognitive task performance (3) Side effects and tolerability.

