A4. Power calculation and sample size Cannabis Withdrawal. We hypothesize that clonazepam will decrease symptoms of cannabis withdrawal (e.g. ,irritability, sleep efficiency). With a sample size of 80, the test of a single contrast at the 0.050 level will have >90% power to detect a 25% decrease in these ratings under conditions of medication administration compared to placebo, assuming the same between-level correlation and SD than our earlier studies. Cannabis Relapse: The time to relapse as recorded by the Timeline Follow Back method and confirmed by creatinine-normalized quantitative urine THC levels, or time to dropout of study, whichever comes first (survival outcome). The sample size of 80 was chosen to ensure sufficient power (at least 80%) of a two-sided test with level of significance 5% for detecting difference between the two experimental treatments with respect to time to relapse, based on the Cox proportional hazards model. We expect that the clonazepam group will have greater time to sustained relapse than the placebo group. The rate of survival for the placebo group can be expected to be 15% based on our prior studies. With 40 per arm, we will be able to detect a difference in proportion of surviving in placebo versus clonazepam of approximately 27% (i.e. 15% on placebo vs 41.81% on clonazepam). This corresponds to a hazard ratio of 0.46 (Machin et al. 1997). The power computation was performed assuming that the covariates (i.e., baseline cannabis

use and age) do not have any predictive power. If they do, the power of the primary hypothesis will be higher than 80%. The 26.81% rate difference is consistent with a medium to large sized effect, which is what we are seeking in this early Phase II trial. This represents an effect that would be clinically meaningful and likely to make a substantial impact on the success of clonazepam treatment in clinical practice. The proposed sample size n=40 for clonazepam group will also enable us to estimate the relapse and retention rates of the treatment group with a 95% confidence interval, $\pm 15.5\%$, in the worst case.

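### SAP C3 leaves two candidate analyses for the inpatient withdrawal outcome and does not say which decides; the one it names drops patients with a missing day, against its own ITT rule

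*SAP*

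**What the plan says.** SAP section A2 lists cannabis withdrawal (mood, sleep, food intake) first among the primary outcomes. The protocol's Study Procedures place the inpatient withdrawal measurements on days 2 to 5, and Table 1 shows two groups, clonazepam and placebo.

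Four statements in SAP section C3 bear on how these data are analysed:

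- Model: "Subjective effects, food intake, sleep, and task performance will be analyzed using repeated measures analysis of variance (ANOVA) models".
- Error term: "Planned contrasts will be single degree of freedom comparisons using the appropriate interaction error term". No between-patient or within-patient factors are listed.
- Sample: "The primary analyses in this study will be on the intent-to-treat (ITT) sample, i.e. on all randomized patients".
- Missing data: "We will account for unobserved data by examining the primary outcome variables using longitudinal mixed effects models". The sentence before this one is about cannabis consumption and abstinence.

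On power for withdrawal, section A4 says that with 80 patients "the test of a single contrast at the 0.050 level will have >90% power to detect a 25% decrease" on medication compared with placebo, "assuming the same between-level correlation and SD than our earlier studies". Its relapse paragraph fixes the layout: "With 40 per arm, we will be able to detect a difference in proportion of surviving in placebo versus clonazepam".

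**The concern.** Two analyses can be claimed for one primary outcome. The ANOVA sentence names the inpatient measures. The mixed-model sentence covers them if primary outcome variables means the A2 list, but not if it refers only to the cannabis-use variables just mentioned. Nothing says which result decides. The choice matters as soon as a patient misses a day: classical repeated-measures ANOVA needs a complete row per patient, so it would leave randomised patients out of a primary intent-to-treat analysis.

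The error term adds a second uncertainty. Each patient receives clonazepam or placebo, never both. An interaction error (day by subject within arm) suits group-by-day contrasts. The average clonazepam-placebo difference, which A4's wording describes, has to be judged against variation between patients, and C3 does not name that term.

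At stake are a weaker and somewhat diluted withdrawal estimate, and room to choose the analysis after seeing the data.

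**Working it through.** **1. The plan's own power figure.** A4 gives no placebo mean, SD or correlation, and no scale or time point, so the power above 90% can be neither reproduced nor refuted. What it would require can be computed. For a two-sample t test (noncentral t, 40 per arm, two-sided 0.05), 90% power needs a difference of 0.734 SD of the analysed score.

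- One score per patient: a 25% decrease qualifies if the SD is at most 0.25/0.734 = 34% of the placebo mean.
- Mean of four days with between-day correlation ρ: the SD shrinks by √((1+3ρ)/4) = 0.689, 0.791 or 0.880 at ρ = 0.3, 0.5 or 0.7. The detectable difference in single-day SDs is 0.734 times this, or 0.51, 0.58 or 0.65. The single-day SD may then be up to 49%, 43% or 39% of the placebo mean.

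The unstated inputs decide the answer. At an SD of 50% of the mean and ρ = 0.5, power is about 60% on one score and 80% on a four-day mean in parallel arms. A within-patient contrast on 80 patients, which this design does not have, would give 99%.

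**2. Complete data.** In three balanced trial data sets, the patient-level ANOVA t and the random-intercept mixed-model t were the same: −1.439, −1.724 and −2.413 by both methods. Without missing days, nothing turns on the choice.

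**3. Missing days.** Simulation with 3,000 runs per row. All settings are assumptions: 40 per arm, one score per day for four days, ρ = 0.5, true effect −0.580 single-day SD (90% power on complete four-day means), and no return after leaving. The logit of leaving is c + 1.0 × the previous day's score, with c = −4.3, −3.5 or −2.85.

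| Patients missing at least one day | Complete-case estimate | Share of true effect | Complete-case power | Mixed-model estimate | Mixed-model power |
|---|---|---|---|---|---|
| 4.9% | −0.563 | 0.563/0.580 = 97% | 87.8% | −0.579 | 90.0% |
| 10.1% | −0.547 | 0.547/0.580 = 94% | 84.4% | −0.578 | 89.7% |
| 17.3% | −0.531 | 0.531/0.580 = 92% | 80.0% | −0.579 | 89.2% |

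High scorers leave more often, and more of them are on placebo, so the remaining placebo patients look better and the difference shrinks. With no true effect and the same c, type I error is 4.7%, 4.8% and 5.2% for complete cases, and 4.8%, 4.7% and 4.5% for the mixed model. The harm is lost power and dilution, not false positives.

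**4. Error term, if misused.** With four days and one score per day, the between-patient mean square exceeds the day-by-subject mean square by the ratio (1+3ρ)/(1−ρ) = 2.7, 5.0 or 10.3 at ρ = 0.3, 0.5 or 0.7. The day-by-subject error has 3 × 78 = 234 degrees of freedom. Testing the average arm difference on it gives type I error P(F(1,234) > Fcrit/ratio) = 23%, 38% or 54%. On patient-level error it is 5%.

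**The case against.** **The error term.** A reader might infer that C3 prescribes a test with inflated type I error. The text does not support that. C3 says the appropriate interaction error, directly after a sentence on the Huynh-Feldt correction, which concerns within-patient effects. Contrasts on such an error are naturally group-by-day contrasts, for which it is valid, and a standard ANOVA with a between-patient factor tests that factor on patient-level error anyway. C3's mention of peak ratings also suggests several ratings per session, so there may be more than one interaction term to choose among. The 23% to 54% describes a conditional misuse.

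**Patient-level variation.** It would be wrong to say that the SAP lacks it. Model (3) under Hypothesis 4 has a random intercept per patient, and Hypothesis 5 applies it to the Marijuana Withdrawal Checklist, which the protocol calls the primary measure of withdrawal. But that model covers weekly scores over weeks 1 to 12 and is worded for nabilone and XR-NTX. It does not reach inpatient days 2 to 5.

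**Missing data.** On the wider reading of the mixed-model sentence, C3 already handles missing days, and it plans a sensitivity analysis for missing at random. That reading is available, but it is not the only one, and C3 names ANOVA for these measures. It is also true that no inpatient loss rate is given. The 60 completers out of 80 in the protocol cover the whole trial and cannot be read as a 25% inpatient loss.

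**Power.** A reader might infer that the figure above 90% is wrong or that 80 patients are too few. Neither follows. The figure is attainable for plausible inputs, the inputs may stand in parts of the grant not reproduced here, and A4 says that 80 was chosen for relapse.

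**Conclusion.** The point holds as a gap in the specification of a primary outcome's analysis. C3 names classical ANOVA for the inpatient withdrawal measures, allows a mixed-model reading of the same outcome, and does not say which decides. The ANOVA route conflicts with the all-randomised sample whenever a day is missing.

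The size depends on undocumented inpatient loss. It is nil with complete data. Under the assumed score-dependent loss it is about 2 power points at 5% of patients and about 10 at 17%, with the estimate diluted by about 3% to 8%. These figures rest on correlation 0.5, one score per day and the assumed dropout model.

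The error-term wording is a risk to close, not a demonstrated error. The A4 power figure is missing detail, not a wrong number. Neither would justify a change in sample size.

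**What to change.** In C3, make one mixed model the deciding analysis of the inpatient day 2 to 5 withdrawal measures:

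- group, day and group-by-day, with the covariates that SAP sections 3.a.iii and 3.d already require in all models;
- a patient random effect and all randomised patients;
- the clonazepam-placebo contrast tested at patient level, and the interaction error term limited to group-by-day contrasts;
- the repeated-measures ANOVA kept as supportive.

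As a minor clarification in A4, state the measure, time point, placebo mean, SD and correlation (and between what) taken from the earlier studies. If a standardised effect is quoted, say which SD it uses: 40 per arm gives 90% power for 0.73 SD of the analysed score, which for a four-day mean is about 0.51, 0.58 or 0.65 single-day SDs at correlation 0.3, 0.5 or 0.7.

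The cost is a few lines of SAP text and one recalculated power statement, with no new data or patients. The stated power may turn out less favourable. The mixed model relies on missing at random, for which C3 already plans a sensitivity analysis.
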